8. DATA MANAGEMENT AND STATISTICAL ANALYSIS

8.1. Data Management and Quality Assurance Considerations

This study will employ eCRFs. The site will be trained on specific forms and procedures for source documentation and maintenance of an audit trail of the data that is entered on the eCRF prior to study initiation.

Study personnel at each site will enter data from source documents corresponding to a subject's visit into the protocol-specific eCRF when the information corresponding to that visit is available. Subjects will not be identified by name in the study database or on any study documents to be collected by the Sponsor (or designee), but will be identified by subject number (6 digits: the first 3 for the institution and the last 3 for the subject).

The Investigators will prepare and maintain adequate and accurate source documents designed to record all observations and other pertinent data for each subject treated with the study drug.

If a correction is required for an eCRF, the time and date will be recorded by the person updating eCRF data to create an audit trail. The Investigator is responsible for all information collected on subjects enrolled in this study. All data collected during the course of this study must be reviewed and verified for completeness and accuracy by the Investigator.

Queries will be issued for any inconsistencies, omissions, and discrepancies and will be resolved by the appropriate parties.

Database lock will occur once quality assurance procedures have been completed.

The statistical analysis of these data will be performed by the Sponsor or designee. All AEs will be coded using the latest version of the Medical Dictionary for Regulated Activities (MedDRA). Concomitant medications will be coded using the latest version of the World Health Organization Drug Dictionary.

All procedures for the handling and analysis of data will be conducted using good computing practices meeting FDA, European Medicines Agency, and ICH guidelines for the handling and analysis of data for clinical studies. Data management details will be outlined in a separate data management plan.

8.2. Sample Size

Up to 76 subjects per treatment arm provides 90% power to detect ES of 0.53 and 80% power to detect ES of 0.46. This level of ES is the minimum amount considered clinically relevant treatment effect and is less than the effect size seen in the Phase 2a studies; therefore, provides a statistical buffer to achieve a positive outcome, if the magnitude of treatment effect by chance is lower in the present study.

8.3. Analysis Sets

The safety analysis set will include any subject who receives at least 1 dose of study drug.

The efficacy analysis set will include any subject who receives at least 1 dose of study drug and has at least 1 post-dose HVLT-R assessment.

8.4. Pharmacokinetics (PK)

Trough and maximum concentrations (C_{Trough} and C_{max} , respectively) will be evaluated on Day 21 (i.e.; at steady-state) for each subject and descriptive statistics for the neflamapimod treatment group will be presented. In addition area under the time concentration curve (AUC) will be derived utilizing population PK methods utilizing drug concentration data from Day 21 as well the sparse sampling on Days 42 and 84. C_{Trough} , C_{max} and AUC will be correlated to CYP2C19 genotype status. In addition, a PK/PD model for neflamapimod and effects on HVLt-R, WMS, CDR-SB, and/or CSF biomarkers will be developed *post hoc* based on the available data.

8.5. Efficacy

8.5.1. Primary Efficacy Variables

The primary efficacy variable is:

- Combined change in z-scores of total recall and delayed recall on the HVLt-R in neflamapimod-treated subjects compared to placebo-recipients.

To obtain a single statistic, the total recall and delayed recall scores will be converted to z-scores and the combined change in z-scores will be compared for the two treatment groups. Specific statistical analyses for efficacy variables will be identified in a prospective Statistical Analysis Plan.

8.5.2. Secondary Efficacy Variables

The secondary efficacy variables are:

- Change from Baseline to Week 24 in recall and recognition of the WMS, CDR-SB, MMSE, and CSF biomarkers (total tau, p-tau₁₈₁, A β ₁₋₄₀, A β ₁₋₄₂, neurogranin, neurofilament light chains) comparing neflamapimod-treated subjects with placebo-recipients.

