Following completion of informed consent procedures, subjects will enter the Screening phase of the study.

Two Screening visits are planned to allow most screening procedures to be completed and reviewed during the first visit before lumbar puncture to collect CSF is performed during Screening Visit 2.

Once eligibility is confirmed and before the first dose of study drug, subjects will be randomly assigned on 1:1 basis to placebo or neflamapimod treatment. Investigators and subjects will be blinded to the treatment assignment.

Dosing will start on Day 1 following completion of all Baseline procedures.

During the treatment period, subjects will return to the clinic on Days 21, 42, 84, 126, and 168. Telephone contacts will be conducted to determine subject status and assess compliance between Days 42 and 84 (Visits 5 and 6); Days 84 to 126 (Visits 6 and 7); and Days 126 and 168 (Visits 7 and 8).

Episodic memory and other cognitive assessments will be performed at Baseline and Days 42, 84, and 168.

Lumbar puncture will be performed, and CSF collected at Screening Visit 2 and on Day 168.

A Follow-up visit will be conducted 14 (± 3) days following the last dose of study drug.

TABLE OF CONTENTS

SPONSOR PROTOCOL APPROVAL PAGE	2
INVESTIGATOR’S SIGNATURE OF AGREEMENT PAGE	3
SPONSOR CONTACT INFORMATION	4
SYNOPSIS	5
TABLE OF CONTENTS	9
LIST OF TABLES	12
LIST OF ABBREVIATIONS	13
1. INTRODUCTION	15
1.1. Scientific Rationale	15
1.2. Pre-Clinical Pharmacology Results	16
1.3. Prior Clinical Experience	16
2. OBJECTIVES	20
2.1. Primary Objective	20
2.2. Secondary Objectives	20
3. INVESTIGATIONAL PLAN	21
3.1. Overall Study Design and Plan	21
3.1.1. Screening.....	21
3.1.2. Treatment Period	21
3.1.3. Follow Up.....	21
3.1.4. Early Discontinuation.....	21
3.2. Discussion of Study Design	21
3.2.1. Rationale for Dose Selection	22
4. SELECTION OF STUDY POPULATION	24
4.1. Inclusion Criteria	24
4.2. Exclusion Criteria	24
4.3. Removal of Subjects from Treatment	25
5. TREATMENTS ADMINISTERED	27
5.1. Packaging and Labeling	27
5.2. Study Drug Supply, Storage, and Handling	27
5.3. Drug Accountability, Disposal, Return, or Retention of Unused Study Drug	27
5.4. Method of Assigning Subjects to Treatment Group	28
5.5. Study Blinding and Breaking the Blind	28

5.6.	Dose Modification for Toxicity	28
5.7.	Prior and Concomitant Therapy	28
5.8.	Contraception and Pregnancy	30
5.9.	Activity Restrictions	31
5.10.	Treatment Compliance.....	31
6.	STUDY ASSESSMENTS AND PROCEDURES	32

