3.1.3. Follow Up

A Follow-up Visit will be conducted 14 (± 3) days following the last dose of study drug.

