- e. Informed consent procedures, including signing of informed consent, must be completed before any study-specific procedures are performed.
- f. Female subjects who have reached menopause in the previous year must have a serum or urine pregnancy test performed during Screening; subjects with positive results are not eligible for study participation.
- g. Refer to [Section 6.2.9](#) for details regarding physical examination.
- h. Definitions and procedures for documenting and reporting AEs serious adverse events (SAEs) are provided in [Section 7](#).
- i. Details of clinical laboratory sampling for chemistry, hematology, and coagulation studies are discussed in [Section 6.2.11](#).
- j. Details of 12-lead ECG assessment are discussed in [Section 6.2.10](#).
- k. Refer to the following sections for details of cognitive assessments [Section 6.2.6](#) (MMSE, CDR), and [Section 6.2.7](#) (NTB – HVLT-R/WMS).
- l. MRI/CT results should be available and reviewed before lumbar puncture is performed.
- m. Perform lumbar puncture (LP) only after subject has been deemed eligible based on all other inclusion/exclusion criteria, e.g. MRI, labs etc. Refer to [Section 6.2.4](#) for details regarding LP.
- n. LP is to be performed within ± 2 days of the last study drug dose.
- o. LP need not be performed at the ET visit for patients who discontinue prior to Visit 5 (Day 42).
- p. Study drug details including packaging, storage, accountability, and dosing are presented in [Section 5](#).
- q. Refer to [Section 6.2.8](#) for details regarding PK sampling.
- r. CYP2C19 genotyping is mandatory; testing for apolipoprotein E is optional. (Apolipoprotein E results may be disclosed to subject at the end of the study.)

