6.2.6. Mini-Mental State Examination/CDR

The MMSE (Folstein et al, 1975) consists of 11 tests of orientation, memory (recent and immediate), concentration, language, and praxis. Scores range from 0 to 30, with lower scores indicating greater cognitive impairment. It is based on the performance of the subject and takes approximately 5 to 10 minutes to administer.

The CDR (Hughes, 1982) is a semi-structured interview resulting in a semi-quantitative scoring of cognitive impairment in milder and more progressed forms of dementia. It is sensitive in both AD dementia and Mild Cognitive Impairment (MCI), and is an approved regulatory endpoint recognized by the FDA. The CDR interview is to be conducted with the subject and Caregiver by an experienced and certified clinician. The CDR yields both a global and an SB score. The global CDR rating, along with the memory box score, will be used to determine a subject's eligibility for inclusion. In addition, the CDR-SB score will be utilized to evaluate cognitive and functional changes from baseline to Visit 6 and Visit 8.

Standardized MMSE (Version 2.0) and CDR will be conducted by the Investigator or designee.

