#### 3.2 Secondary Endpoints

The secondary efficacy variables at Week 24 and follow-up when applicable are:

- Change in WMS immediate and delayed recall composites in neflamapimod-treated subjects compared to placebo-recipients.
- Change in CDR-SB in neflamapimod-treated subjects compared to placebo-recipients.
- Change in MMSE in neflamapimod-treated subjects compared to placebo-recipients
- Change in CSF biomarkers [total tau (T-tau), P-tau181, A $\beta$ 1-40, A $\beta$ 1-42, neurogranin, neurofilament light chain] in neflamapimod-treated subjects compared to placebo-recipients at the end of treatment.

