### 6.2.2 Baseline and Change from Baseline

Baseline is defined as the last non-missing value (either scheduled, unscheduled or repeat) before the subject receives first dose of study drug (Day 1). Visit 3 (Day 1) date is defined as the date of the first dose.

Baseline score of MMSE for each subject is calculated using the average of Screen and Day 1 measurements.

Change from baseline  $CHG = AVAL - BASE$  where  $AVAL$  is the post-baseline value,  $BASE$  is the baseline value.

Baseline z-score will be used as a covariate in the MMRM and ANCOVA analysis. It will be calculated as below:

For baseline total recall, a z-score for each subject is defined by  $z = (x - m) / s$  where  $x$  is the subject's total recall at baseline, and  $m$  and  $s$  are the overall mean and overall standard deviation of total recall at baseline across all subjects. Similarly, a baseline z-score for each subject for delayed recall can be calculated.

A composite baseline z-score for each subject is calculated using equal weighting in the following way:

$Z = 0.5 * z\text{-score for total recall at baseline} + 0.5 * z\text{-score for delayed recall at baseline}$ .

The calculation method can be referenced to [Section 6.2.12](#).

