#### 6.10.4 Secondary Analyses

The secondary efficacy endpoints at Week 24 and follow-up when applicable are:

- Change in WMS immediate and delayed recall composites in neflamapimod-treated subjects compared to placebo-recipients.
- Change in CDR-SB in neflamapimod-treated subjects compared to placebo-recipients.
- Change in MMSE in neflamapimod-treated subjects compared to placebo-recipients.
- Change in CSF biomarkers (T-tau, P-tau181, A $\beta$ 1-40, A $\beta$ 1-42, neurogranin, neurofilament light chain) in neflamapimod-treated subjects compared to placebo-recipients at the end of treatment.

The same method used for the primary efficacy analysis will be applied for the analyses of the change in WMS and change in CDR-SB.

Changes in MMSE and CSF biomarkers will be compared using an analysis of covariance (ANCOVA) with treatment group, background AD-specific therapy, CDR-Global Score as main effects and the baseline assessment as the covariate. The results of the ANCOVA will be summarized using the treatment groups' least square means, the difference between the treatment groups' least square means, the 95% confidence interval for the treatment group difference and the p-value. Scale Plots of Mini-Mental State Examination (MMSE) Score by Visit and by Treatment; and Baseline and Change from Baseline to Day 84 MMSE Score.

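### MMSE change is defined as a Week 24 secondary endpoint, but the visit schedule collects no MMSE at Week 24 or at early termination

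*Protocol*

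**What the plan says.** Protocol 8.5.2 gives one time point for all secondary variables: "Change from Baseline to Week 24 in recall and recognition of the WMS, CDR-SB, MMSE, and CSF biomarkers". SAP 3.2 introduces its list with "The secondary efficacy variables at Week 24 and follow-up when applicable are", and SAP 6.10.4 repeats that timing. MMSE change is on both lists.

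The MMSE row of Protocol Table 6-1 is marked at Screening Visit 1, Visit 3 (Day 1), Visit 6 (Day 84) and the Follow-up visit. It is blank at Visit 8 (Day 168) and at the early termination (ET) visit. Under Protocol 3.1.3, Follow-up takes place 14 (±3) "days following the last dose of study drug".

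Three other passages bear on MMSE timing:

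- The protocol synopsis states "Episodic memory and other cognitive assessments will be performed at Baseline and Days 42, 84, and 168". It does not name MMSE.
- Protocol 6.2.6 says "the CDR-SB score will be utilized to evaluate cognitive and functional changes from baseline to Visit 6 and Visit 8". It names no post-baseline visit for MMSE.
- SAP 6.10.4 analyses MMSE change by ANCOVA without naming a visit, and then asks for a plot of "Baseline and Change from Baseline to Day 84 MMSE Score".

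**The concern.** An endpoint needs a scheduled measurement at its defining time point, and MMSE has none. Two quite different quantities could fill the gap: a score halfway through treatment (Day 84), or a score taken about two weeks after drug was stopped. Neither is the effect after 24 weeks of treatment. Because the ANCOVA names no visit, the choice stays open until someone programs the table, possibly after results are known, and the number chosen would then stand for an endpoint listed at Week 24.

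The secondary objective pairs MMSE with CDR-SB, so readers will expect to compare the two. Under the schedule, Day 84 is their only common post-baseline visit. The same is true of MMSE with HVLT-R and WMS. Subjects who stop early have no end-of-treatment MMSE, although HVLT-R, WMS and CDR are all collected at their ET visit.

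**Working it through.** The point concerns scheduling, so the check is to compare passages, with some day arithmetic. The plan's only computed figure here is its power statement (76 per arm, two-sided 5%). It reproduces: a two-sample t-test gives 90.1% at an effect size of 0.53 and 80.4% at 0.46, against the stated 90% and 80%. Nothing below depends on it.

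**Step 1. Read Table 6-1 across its ten visit columns** (V1, V2, V3 Day 1, V4 Day 21, V5 Day 42, V6 Day 84, V7 Day 126, V8 Day 168, ET, Follow-up).

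| Row | Visits marked | Day 168? | ET? |
|---|---|---|---|
| MMSE | V1, Day 1, Day 84, Follow-up | No | No |
| HVLT-R and WMS | Day 1, Day 42, Day 84, Day 168, ET | Yes | Yes |
| CDR | V1, Day 84, Day 168, ET | Yes | Yes |
| Lumbar puncture | V2, Day 168, ET | Yes | Yes |

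**Step 2. Rule out a column shift in the table text.** The other rows, read in the same way, agree with the body text. CDR falls at Visits 6 and 8, as in Protocol 6.2.6. HVLT-R and WMS fall at Days 42, 84 and 168, as in the synopsis. Lumbar puncture falls at Screening Visit 2 and end of treatment, as in Protocol 6.2.4. The SAP independently supports the MMSE row: under SAP 6.2.2, "Baseline score of MMSE for each subject is calculated using the average of Screen and Day 1 measurements", which matches the first two marks, and the SAP 6.10.4 plot to Day 84 matches the third. The SAP also analyses MMSE by ANCOVA while giving WMS and CDR-SB the repeated-measures model.

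**Step 3. Distance from Week 24.**

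- Week 24 is Day 24 × 7 = 168, with a visit window of 168 ± 5, that is Day 163 to 173.
- The Day 84 score is 168 − 84 = 84 days early.
- For a completer whose last dose is at Visit 8, Follow-up is nominally Day 168 + 14 = 182 (182 / 7 = Week 26). Its earliest day is 163 + 11 = 174 and its latest is 173 + 17 = 190. The range 174 to 190 lies wholly outside the Day 163 to 173 window, and the subject is 14 ± 3, so 11 to 17, days off drug.
- For an early discontinuer with last dose on Day *d*, Follow-up falls between *d* + 11 and *d* + 17. With last dose on Day 42, that is Day 53 to 59. Follow-up scores therefore do not share a common time since randomization.

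**Step 4. Look for a rule that fills the gap.** SAP 6.2.16 moves ET efficacy data to the next scheduled visit, but no MMSE is taken at ET. SAP 6.10 rules out imputing missing efficacy data. SAP 6.2.18 describes when Follow-up occurs but does not map it to Week 24. SAP section 9 records no departure from the protocol analysis. The planned MMSE ANCOVA outputs (overall, Table 14.2.2.7; subgroups, Tables 14.2.6.7, 14.2.6.13.3 and 14.2.6.17.3) carry no visit in their titles. No rule supplies a Week 24 value or picks a substitute.

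**The case against.** The strongest reply is that the SAP already covers this. Its list allows for follow-up where applicable, and MMSE is the only listed secondary measure that Table 6-1 schedules at Follow-up, so the phrase may well have been written for it. The synopsis endpoint list gives MMSE no time point at all. On this reading only Protocol 8.5.2 is strictly contradicted. That is a fair reading, but at most it permits an off-drug analysis. It does not produce a Week 24 value, and it leaves the ANCOVA visit unnamed.

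A second reply is that the synopsis puts other cognitive assessments at Day 168, and the Table 6-1 footnote beginning "Refer to the following sections for details of cognitive assessments" counts MMSE among them, so MMSE was meant to be done there. If so, the synopsis and Table 6-1 disagree, which is a further reason to reconcile them. The sentence is also loose, since neither MMSE nor CDR is scheduled at Day 42.

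Third, SAP 6.10.7 treats all secondary endpoints as descriptive, and the primary test, its alpha and the sample size are untouched. This stands and lowers the priority, but a descriptive endpoint still needs a defined and collected time point.

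Fourth, no output title calls the MMSE result a Week 24 result, and the MMSE figure is presented by visit. So mislabelling is a risk left open rather than something the plan instructs. Early discontinuers are also asked to attend Follow-up, so they may have a post-treatment MMSE. What they lack is one at the end of treatment.

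Finally, the SAP's July 2019 revisions sit beside text describing randomization in the past tense, so adding a Day 168 test may come too late for some or all subjects. That affects which remedy is feasible, not whether one is needed.

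**Conclusion.** The concern holds. As Protocol 8.5.2 defines it, MMSE change to Week 24 cannot be computed from the scheduled data for any of the approximately 152 subjects. MMSE change can be computed at Day 84 or at Follow-up, but these are different quantities and the plan does not choose between them. The conclusion rests on the Table 6-1 row being as printed, which the other rows and the SAP's own MMSE wording support, and on no unscheduled MMSE being taken at Visit 8. The effect is confined to one secondary endpoint and its subgroup tables. It should be settled before unblinding, because the unnamed visit is otherwise a choice made with results in hand.

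**What to change.** Make the endpoint, the schedule and the analysis name the same visit.

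**If collection is still open:** mark MMSE at Visit 8 (Day 168) and at ET in Table 6-1, and name Day 168 as the ANCOVA visit in SAP 6.10.4 and in the MMSE table titles. Moving the Follow-up test to Day 168 leaves the number of administrations for a completer unchanged. Adding Day 168 and keeping Follow-up preserves the off-drug score. State also that the SAP 6.2.16 rule sends an ET MMSE to the next visit at which MMSE is scheduled. The cost is a minor protocol amendment and a test that Protocol 6.2.6 puts at 5 to 10 minutes, at a visit subjects already attend for HVLT-R, WMS and CDR. Subjects already past Day 168 would still lack the value, and the report should say how many there are.

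**If collection cannot change:** restate the MMSE endpoint in Protocol 8.5.2 and SAP 3.2 and 6.10.4 as change to Day 84, name Day 84 in the ANCOVA and its subgroup versions, report the Follow-up score separately as off-treatment, and record the change in SAP section 9. This costs only wording.

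Under either option, reword the synopsis sentence on cognitive visits so that it says which tests are done on which days.

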8.6. Safety

The incidence of treatment-emergent AE and SAEs the causal relationship between an AE/SAE and the Study Drug and severity will be tabulated by treatment (dose) group.

Individual clinically-significant changes in clinical laboratory and ECG parameters will be listed along with median and mean and standard deviation by treatment group.

8.7. Interim Analysis

No interim analysis is planned. Only pharmacokinetic data will be monitored by an independent clinical pharmacologist on an every 3-month basis without any reference to other study data or subject identification, with the exception of baseline demographics (age, weight, race) and CYP2C19 genotype.

9. STUDY MANAGEMENT

9.1. Ethics and Consent

9.1.1. Regulations and Guidelines

The study will be performed in accordance with this protocol, US Investigational New Drug Application regulations (21 CFR 312) or local national laws (as applicable) and ICH guidelines for Good Clinical Practice. These guidelines are on file at Worldwide Clinical Trials.

9.1.2. Institutional Review Boards/Independent Ethics Committees

Conduct of the study must be approved by an appropriately constituted IRB or IEC. Approval is required for the study protocol, investigational drug brochure, protocol amendments, ICFs, subject information sheets, and advertising materials. No investigational product will be shipped to a site until written IRB/IEC authorization has been received by the Sponsor or its designee.

9.1.3. Informed Consent

For each study subject, a written ICF will be obtained before any protocol-related activities. As part of this procedure, the Investigator or a designated representative must explain orally and in writing the nature, duration, and purpose of the study, and the action of the investigational product in such a manner that the subject and (if applicable) appointed guardian are aware of the potential risks, inconveniences, or adverse effects that may occur. Subjects should be informed that they may withdraw from the study at any time. They will receive all information that is required by local regulations and ICH guidelines. The Investigator or a designated representative will provide the Sponsor or its designee with a copy of the IRB/IEC-approved ICF before the start of the study.

